1.23 LOST TO FOLLOW-UP

A participant will be considered lost to follow-up if he or she fails to return for the 2 scheduled follow up Otolaryngology clinic visits and is unable to be contacted by the study site staff.

The following actions must be taken if a participant fails to return to the clinic for a required study visit:

- The site will attempt to contact the participant and reschedule the missed visit within 2 weeks and counsel the participant on the importance of maintaining the assigned visit schedule.
- Before a participant is deemed lost to follow-up, the investigator or designee will make every
 effort to regain contact with the participant (where possible, 3 telephone calls and, if necessary,
 a certified letter to the participant's last known mailing address or local equivalent methods).
 These contact attempts should be documented in the participant's medical record or study file.
- Should the participant continue to be unreachable, he or she will be considered to have withdrawn from the study with a primary reason of lost to follow-up.

In an effort to minimize failure to follow up, we will incentivize subject with a \$50 payment, to be provided at the follow up visits.

STUDY ASSESSMENTS AND PROCEDURES

1.24 EFFICACY ASSESSMENTS

The primary outcome measure is olfactory ability at 1 and 3 months, measured via the SIT, in head trauma patients. Patients will be identified from the population admitted for observation at Ryder trauma following TBI. Co-investigators on this protocol oversee the trauma unit, round on the admitted patients on a daily basis, and will therefore identify candidates as those patients sustaining a TBI from blunt head injury requiring overnight observation. Relevant standard of care data from the chart will be collected in a HIPPA-compliant fashion, to specifically include (1) history describing mechanism of injury, (2) results of head CT and (3) physical exam upon presentation, with Glascow Coma Score or other standard head trauma assessment details. No additional imaging is required for the study or efficacy measure; however imaging obtained as part of standard routine care available in the medical record will be reviewed. Those patients with severe poly-trauma and/or ongoing intubation or inability to participate in the SIT test will be excluded. The candidate patients will be administered the Brief SIT to assess olfaction. Those with abnormal scores will be offered enrollment in the study. There are only 3 procedures involved in the study to assess efficacy: (1) SIT measures (2) Administration of study medication or placebo, (3) the QOD quality of life questionnaire.

- The SIT is a self-administered 40-item test involving microencapsulated (scratch-and-sniff) odors with a forced-choice design. There are 4 booklets with 10 questions each, asking the subject to identify which of 4 answers best described the odor. Total scores are categorized, based on normative data, as normal, mild hyposmia, moderate hyposmia, severe hposmia, total anosmia, or probable malingering. The test was developed at University of Pennsylvania as part of an NIH-funded program project and is widely used as a standard assessment of olfactory function. We will use the Brief Smell Identification Test that is a rapid and effective 5 minute test during the Screening Visit. This item version of the Smell Identification Test is useful for detecting smell loss in situations where less than five minutes of time is available. For the follow up Visit 2 and Visit 3, we will use the full SIT.
- The QOD is a validated olfactory-specific quality of life questionnaire and is attached.

1.25 SAFETY AND OTHER ASSESSMENTS

Screening for, or participation in, this study will not alter head trauma standard of care. The potential patient safety issue for the study is the possibility of adverse reaction to study medication. The dosage regimen we are using has been used in a previous published trial with no adverse events reported. Nonetheless, we are giving the initial loading dose prior to discharge, which will enable us to identify any immediate events such as acute allergic reaction. Patients will receive instructions and contact information to inform the coordinator or PI promptly of any potential problems. At follow up visit, we will collect patient drug logs and any comments or notes regarding possible side effects.

1.26 ADVERSE EVENTS AND SERIOUS ADVERSE EVENTS

1.26.1 DEFINITION OF ADVERSE EVENTS (AE)

Adverse event means any untoward medical occurrence associated with the use of an intervention in humans, whether or not considered intervention-related (21 CFR 312.32 (a)).

1.26.2 DEFINITION OF SERIOUS ADVERSE EVENTS (SAE)

An adverse event (AE) or suspected adverse reaction is considered "serious" if, in the view of either the investigator or sponsor, it results in any of the following outcomes: death, a life-threatening adverse event, inpatient hospitalization or prolongation of existing hospitalization, a persistent or significant incapacity or substantial disruption of the ability to conduct normal life functions, or a congenital anomaly/birth defect. Important medical events that may not result in death, be life-threatening, or require hospitalization may be considered serious when, based upon appropriate medical judgment, they may jeopardize the participant and may require medical or surgical intervention to prevent one of the outcomes listed in this definition. Examples of such medical events include allergic bronchospasm requiring intensive treatment in an emergency room or at home, blood dyscrasias or convulsions that do not result in inpatient hospitalization, or the development of drug dependency or drug abuse.

1.26.3 CLASSIFICATION OF AN ADVERSE EVENT

1.26.3.1 SEVERITY OF EVENT

For adverse events (AEs) not included in the protocol defined grading system, the following guidelines will be used to describe severity.

- **Mild** Events require minimal or no treatment and do not interfere with the participant's daily activities.
- **Moderate** Events result in a low level of inconvenience or concern with the therapeutic measures. Moderate events may cause some interference with functioning.
- Severe Events interrupt a participant's usual daily activity and may require systemic drug therapy or other treatment. Severe events are usually potentially life-threatening or incapacitating. Of note, the term "severe" does not necessarily equate to "serious".]

1.26.3.2 RELATIONSHIP TO STUDY INTERVENTION

All adverse events (AEs) must have their relationship to study intervention assessed by the clinician who examines and evaluates the participant based on temporal relationship and his/her clinical judgment.

The degree of certainty about causality will be graded using the categories below. In a clinical trial, the study product must always be suspect.

- Related The AE is known to occur with the study intervention, there is a reasonable possibility that the study intervention caused the AE, or there is a temporal relationship between the study intervention and event. Reasonable possibility means that there is evidence to suggest a causal relationship between the study intervention and the AE.
- **Not Related** There is not a reasonable possibility that the administration of the study intervention caused the event, there is no temporal relationship between the study intervention and event onset, or an alternate etiology has been established.

1.26.3.3 EXPECTEDNESS

PI will be responsible for determining whether an adverse event (AE) is expected or unexpected. An AE will be considered unexpected if the nature, severity, or frequency of the event is not consistent with the risk information previously described for the study intervention.

1.26.4 TIME PERIOD AND FREQUENCY FOR EVENT ASSESSMENT AND FOLLOW-UP

The occurrence of an adverse event (AE) or serious adverse event (SAE) may come to the attention of study personnel during study visits and interviews of a study participant presenting for medical care, or upon review by a study monitor.

All AEs including local and systemic reactions not meeting the criteria for SAEs will be captured on the appropriate case report form (CRF). Information to be collected includes event description, time of onset, clinician's assessment of severity, relationship to study product (assessed only by those with the training and authority to make a diagnosis), and time of resolution/stabilization of the event. All AEs occurring while on study must be documented appropriately regardless of relationship. All AEs will be followed to adequate resolution.

Any medical condition that is present at the time that the participant is screened will be considered as baseline and not reported as an AE. However, if the study participant's condition deteriorates at any time during the study, it will be recorded as an AE.

Changes in the severity of an AE will be documented to allow an assessment of the duration of the event at each level of severity to be performed. AEs characterized as intermittent require documentation of onset and duration of each episode.

PI will record all reportable events with start dates occurring any time after informed consent is obtained until 7 (for non-serious AEs) or 30 days (for SAEs) after the last day of study participation. At each study visit, the investigator will inquire about the occurrence of AE/SAEs since the last visit. Events will be followed for outcome information until resolution or stabilization.

Adverse Event reporting will adhere to all established guidelines, as described below.

1.26.6 SERIOUS ADVERSE EVENT REPORTING

The study clinician will immediately report to the UM Human Subjects Research Office any serious adverse event, whether or not considered study intervention related, including those listed in the protocol or investigator brochure and must include an assessment of whether there is a reasonable possibility that the study intervention caused the event. Study endpoints that are serious adverse events (e.g., all-cause mortality) must be reported in accordance with the protocol unless there is evidence suggesting a causal relationship between the study intervention and the event (e.g., death from anaphylaxis). In that case, the investigator must immediately report the event to the sponsor.

All serious adverse events (SAEs) will be followed until satisfactory resolution or until the site investigator deems the event to be chronic or the participant is stable.

1.26.7 REPORTING EVENTS TO PARTICIPANTS

Any subjects who have not yet completed their first follow up visit will be contacted by phone to inform them of any Serious Adverse Events, if any occur.

1.26.8 EVENTS OF SPECIAL INTEREST

In an effort to minimize failure to follow up, we will give the subject the option If for any specific reason will not be able to attend the Visit 2 and Visit 3 in person we will mail by Certified Mail the full Smell identification Test and the QOD questionnaire and request to be send back to us in the same way (Certified Mail will be cover by the Investigator).

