1.3 SCHEDULE OF ACTIVITIES (SOA)

Procedur Informed conser		X	Day -2 to 0	Enrollment/Baseline	Day 0	Home treatment	Day 1-6	Study Visit 2	Day 30 +/-7 days	Study Visit 3	Month 4 +/- 3 weeks
Demographics		Х									
Medical history		Χ									
1.3.1.1.1.1	B-IT (Brief olfactio n test)	Х									
1.3.1.1.1.2	SIT (olfactio n test)In person or send by mail.							Х		Х	
1.3.1.1.1.3	QOD (questio nnaire)	Х						Х		Х	
1.3.1.1.1.4	Radiolo gic/Imag ing assessm ent	X									
Randomization		Х									
Physical exam, w	ith nasal	Χ									
endoscopy											
Vital signs		Χ		Χ				Χ		Χ	
1.3.1.1.1.5	Concom itant medicati on review	Х		X				Х		Х	
Pregnancy test		Χ									
1.3.1.1.1.6	Adminis ter study interven tion			Х		Х					
1.3.1.1.1.7	Adverse event review and evaluati on			X				X		Х	

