1.17 PREPARATION/HANDLING/STORAGE/ACCOUNTABILITY

1.17.1 ACQUISITION AND ACCOUNTABILITY

Randomization, drug and placebo preparation, and packaging will be done by our Jackson research pharmacy following their established protocols for double-blind studies. When ordered, the loading dose will be administered by nursing staff prior to discharge. The remaining outpatient supply will be delivered by the pharmacy to the Ryder Trauma nursing staff to be provided to the patient, along with instructions, upon discharge. If doses are missed, patients will be instructed to return unused product at their follow up visit.

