1.19 STUDY INTERVENTION COMPLIANCE

The loading dose will be given prior to discharge. The remaining study drug will be taken as an outpatient over the next 6 days. We will ask participants to complete a study drug log to record timing of each dose. We will not plan any labs or assays for verification. Drug log will be collected at the first outpatient visit.

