1.22 PARTICIPANT DISCONTINUATION/WITHDRAWAL FROM THE STUDY

Participants are free to withdraw from participation in the study at any time upon request.

An investigator may discontinue or withdraw a participant from the study for the following reasons:

- Pregnancy
- Significant study intervention non-compliance
- If any clinical adverse event (AE), laboratory abnormality, or other medical condition or situation occurs such that continued participation in the study would not be in the best interest of the participant
- If the participant meets an exclusion criterion (either newly developed or not previously recognized) that precludes further study participation

The reason for participant discontinuation or withdrawal from the study will be recorded on the NAC Case Report Form (CRF). Subjects who sign the informed consent form and are randomized but do not receive the study intervention may be replaced. Subjects who sign the informed consent form, and are randomized and receive the study intervention, and subsequently withdraw, or are withdrawn or discontinued from the study, will be replaced. Patients who do not complete the full course of study drug/placebo will be noted in the results tables, and they will not be included in the statistical analysis of outcome measures, since this is a simple comparison of SIT score between patients receiving a 1 week course of NAC versus placebo.

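### The mail-in option asks for the SIT and QOD only; no route is stated for the drug log, unused product or active adverse-event inquiry, on which the full-course exclusion and the AE summary rely

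*Combined protocol and SAP*

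**What the plan says.** Section 1.26.8 lets a participant who cannot come to Visits 2 and 3 complete them by post: "we will mail by Certified Mail the full Smell identification Test and the QOD questionnaire", with return by the same route. Two items are named and no others. In the schedule of activities (1.3), the note "In person or send by mail" stands in the SIT row. AE review and concomitant-medication review are also marked at Visits 2 and 3, with no mail or telephone mode.

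The other follow-up data are tied to attendance:

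- Drug log (1.19): "Drug log will be collected at the first outpatient visit".
- Logs and side effects (1.25): "At follow up visit, we will collect patient drug logs and any comments or notes regarding possible side effects".
- Unused product (1.17.1): "If doses are missed, patients will be instructed to return unused product at their follow up visit".
- Active AE inquiry (1.26.4): "At each study visit, the investigator will inquire about the occurrence of AE/SAEs since the last visit".

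Two parts of the plan use these data. Section 1.31.4 reports the number and severity of AEs. Section 1.22 sets an exclusion from the outcome analysis: "Patients who do not complete the full course of study drug/placebo will be noted in the results tables, and they will not be included". Section 1.30, in contrast, names a single analysis set, intention-to-treat, made up of all randomized participants.

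**The concern.** The packet preserves the efficacy endpoints but omits the data needed to interpret them under the plan's own rules.

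On safety, a participant who mails both visits passes from the Day 0 review to the end of the study without a scheduled question about adverse events. Their AEs reach the site only if they report them or seek care. The AE table would then mix actively and passively ascertained participants.

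On efficacy, 1.22 needs to know who completed the course. Section 1.19 plans no assays, so the log and returned product are the only planned adherence sources, and the packet requests neither. The plan does not say how to classify someone who returns an SIT without a log. That decision would be made ad hoc, possibly after the score has been seen.

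**Working it through.** **Step 1. Routes for each item at Visits 2 and 3**

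| Item | In-person route | Route if mailed | Used by |
|---|---|---|---|
| SIT | 1.3, 1.24 | 1.26.8; mail note in 1.3 | Primary endpoint, 1.31.2 |
| QOD | 1.3, 1.24 | 1.26.8 | Secondary endpoint, 1.31.3 |
| Drug log | 1.19, 1.25 | none stated | Full-course exclusion, 1.22 |
| Unused product | 1.17.1 | none stated | Full-course exclusion, 1.22 |
| Active AE inquiry | 1.3, 1.26.4 | none stated; self-report under 1.25 | AE summary, 1.31.4 |
| Concomitant medications at follow-up | 1.3 | none stated | No planned analysis |

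The gap has consequences for the log, the unused product and the AE inquiry. For concomitant medications it is a record-keeping gap only.

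**Step 2. How much dosing the log covers**

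From 1.16.2: one loading dose of 4 g before discharge, then 2 g twice daily for 4 days (8 doses, 16 g) and 1.5 g twice daily for 2 days (4 doses, 6 g). Home dosing is 8 + 4 = 12 of 13 doses, and 16 + 6 = 22 of 26 g. Course completion is therefore almost entirely a matter of home dosing, which only the log and returned product document.

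**Step 3. Reproduce the plan's sample size**

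Inputs from 1.29 and 1.31.1: means 17 and 25 (difference 8), SD 10, two-sided alpha 0.05, power 0.80.

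n per arm = 2 × (1.960 + 0.842)² × 10² / 8² = 2 × 7.85 × 1.5625 = 24.5, rounded up to 25. Adding the 5 per group from the dropout allowance in 1.29 gives 30, so the stated figure reproduces. The exact t-test calculation gives 25.5, or 26 per arm.

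**Step 4. Conditional effect on power**

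The documents give no mail-in rate, so 0% to 30% at both visits is an assumption. Suppose also that every such participant is dropped under 1.22 for want of a log and none is replaced. Two-sided t-test, standardized difference 8/10 = 0.8:

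| Assumed mail-in | n per arm | Power |
|---|---|---|
| 0% | 30 | 0.861 |
| 10% | 30 × 0.9 = 27 | 0.822 |
| 20% | 30 × 0.8 = 24 | 0.774 |
| 30% | 30 × 0.7 = 21 | 0.716 |

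The allowance of 5 per arm is used up at 5/30 = 16.7%. At 25 per arm, power is 0.791 by the t-test and 0.807 by the normal approximation.

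**The case against.** The best reply is that the protocol is silent on remote collection and does not forbid it. The AE and medication rows at Visits 2 and 3 are not waived for mailed visits, and a coordinator could ask for the log by telephone. That is true, but no procedure requires it. The calls in 1.23 are for rescheduling and regaining contact, with no data collection stated.

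A reader might infer more than the documents support, in four ways.

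- **That these data would never be collected.** Section 1.25 gives participants contact details to report problems, 1.21 records details when study drug is stopped for a possible adverse effect, and 1.26.4 also captures events when a participant presents for care or on monitor review. Concomitant medications are recorded at Screening and Day 0. Someone who mails one visit and attends the other can hand in the log and be asked about AEs then. The loss is of active inquiry and of a required log, and it is clearest for those who mail both visits.
- **That mail-in leaves the home-dosing week uniquely unobserved.** The schedule has no contact between Day 0 and about Day 30 for anyone. Clinic attendees are also asked in retrospect; the difference is that they are asked.
- **That analysis or safety rules depend on concomitant medications.** No planned analysis uses them. The only possible link is the withdrawal rule in 1.22 for a newly met exclusion criterion.
- **That power will fall.** Section 1.22 excludes non-completers, not people without a log. Under the ITT set in 1.30 a missing log removes no one. Section 1.22 also replaces participants who withdraw, although it does not clearly cover someone who stays in the study and lacks a log. At 10% mail-in, power would still exceed the planned 0.80.

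What remains is that the packet as specified omits adherence data and active AE inquiry, and that one section uses adherence to decide who is analysed.

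**Conclusion.** The point holds as a gap in specified data collection. For a participant who mails both visits, the plan as written gives passive AE reporting only after Day 0 and no log or unused-dose information. The exclusion in 1.22 cannot be applied to that person on any planned source, and their contribution to the AE summary is not comparable with that of clinic attendees.

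The size is unknown because no mail-in rate is given. The fall in power from 0.86 to about 0.82, 0.77 or 0.72 rests on three assumptions together: 10%, 20% or 30% mail-in at both visits, dropping without replacement, and 1.22 prevailing over 1.30. It is a bound on one scenario, not a forecast. The gap does not invalidate the design, but the missing data are hard to recover later and cheap to request at the time.

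**What to change.** In 1.26.8 and the schedule of activities, add to the same certified-mail packet:

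1. the drug log, with a count of unused doses;
2. a short AE and concomitant-medication form, which staff review on return as they would at a visit;
3. a line for the date the SIT was taken, so that a mailed score can be placed against the visit window.

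In the statistical section, state that a participant who returns the SIT without a log stays in the analysis as randomized, consistent with the ITT set in 1.30. Reconcile the full-course exclusion in 1.22 with 1.30, so that the primary analysis has one population.

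The cost is one or two extra sheets in a packet already being sent. The downside is small: AEs from these participants are self-reported first and need staff review on return. The change does not shorten the recall period for the home-dosing week, which is the same for clinic attendees.

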1.26.9 REPORTING OF PREGNANCY

If pregnancy occurs during the study, this will be reported to the HSRO. The study medication course is only 1 week, however if pregnancy is identified prior to completion of study medication it will be discontinued.

1.27 UNANTICIPATED PROBLEMS

1.27.1 DEFINITION OF UNANTICIPATED PROBLEMS (UP)

The Office for Human Research Protections (OHRP) considers unanticipated problems involving risks to participants or others to include, in general, any incident, experience, or outcome that meets all of the following criteria:

Unexpected in terms of nature, severity, or frequency given (a) the research procedures that are
described in the protocol-related documents, such as the Institutional Review Board (IRB)approved research protocol and informed consent document; and (b) the characteristics of the
participant population being studied;

- Related or possibly related to participation in the research ("possibly related" means there is a reasonable possibility that the incident, experience, or outcome may have been caused by the procedures involved in the research); and
- Suggests that the research places participants or others at a greater risk of harm (including physical, psychological, economic, or social harm) than was previously known or recognized.

